4.6.6.8.2. Analysis Sets

Table GPGV.4.8 summarizes the immunogenicity analysis sets used in the immunogenicity analysis and for safety and efficacy by ADA status analysis.

 Table GPGV.4.8.
 Immunogenicity Analysis Sets

Analysis Set	Population	Description	Post Baseline Period
Immunogenicity Analysis Set 1	mITT	Refer to SS1 for details (Table GPGV.3.1)	Refer to SS1 for details
Immunogenicity Analysis	mITT - TZP-treated participants.	Subset of SS2. Participants who had at least one dose of tirzepatide.	 LY Treatment Period: Data obtained during Double- Blind Period and Open-Label Period, regardless of adherence to study intervention or initiation of rescue antihyperglycemic medication. LY Treatment Period Plus Follow-up Period: Data obtained during Double- Blind Period, Open-Label Period and Safety Follow-up Period, regardless of adherence to study intervention or initiation of rescue antihyperglycemic medication.
	mITT - TE ADA evaluable participants	Subset of EAS1.	Refer to EAS1 for details. This analysis set includes only Week 30 completers.

Abbreviations: EAS1 = efficacy analysis set 1; mITT = modified intent-to-treat; SS1 = safety analysis set 1; SS2 = safety analysis set 2; TE ADA = treatment-emergent antidrug antibodies; TZP = tirzepatide.

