# 9.3.6. Evaluation of Immunogenicity

The frequency and percentage of participants with preexisting ADA, with TE ADA and with neutralizing TE ADA to tirzepatide may be tabulated by tirzepatide dose. Treatment-emergent ADA are defined as those with a titer 2-fold (1 dilution) greater than the minimum required dilution (MRD) if no ADAs were detected at baseline (treatment-induced ADA) or those with a 4-fold (2 dilutions) increase in titer compared to baseline if ADAs were detected at baseline (treatment-boosted ADA). For TE ADA participants, the distribution of maximum titers may be described. The frequency of neutralizing antibodies to tirzepatide and/or cross-reactive and neutralizing antibodies to endogenous counterparts may be tabulated in participants with TE ADA.

The relationship between the presence of antibodies and tirzepatide PK and PD response including safety and efficacy to tirzepatide may be assessed.

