2.1. Type I Error Rate Control Strategy

The 2 estimands of the primary efficacy objectives are intended for different purposes (see rationales in Section 1.1). For that reason, there is no type 1 error rate adjustments to be made for conducting analyses relative to efficacy and treatment-regimen estimands. Moreover, no multiplicity adjustments will be made for conducting separate analyses relative to additional secondary and exploratory efficacy objectives or safety assessments.

Statistical comparisons for the primary and key secondary endpoints will be carried out using a graphical approach (Bretz et al. 2009, 2011) to strongly control the type I error at a 2-sided significance level of 0.05. The graphical approach will be conducted separately for each of the estimands, and each will be tested at the full significance level of 0.05.

The type 1 error control strategy is illustrated on the graphical testing scheme on Figure GPGV.2.1.

Abbreviation: A1c = glycated hemoglobin; BMI = body mass index; CFB = change from baseline; FSG = fasting serum glucose; PCFB = percent change from baseline; SDS = standard deviation score; TZP = tirzepatide.

Figure GPGV.2.1. Graphical testing scheme.

3. Analysis Sets

For statistical analysis purposes, the following participant analysis sets are defined in Table GPGV.3.1.

Table GPGV.3.1. Participants Analysis Sets

Participant Analysis Set	Description
Screened Participants	All participants who sign the Informed Consent Form.
Randomized participants	All participants who are randomly assigned to a treatment arm.
Modified Intent-to-Treat (mITT) population	All randomly assigned participants who are exposed to at least 1 dose of study intervention (that is tirzepatide or placebo).
Efficacy Analysis Set 1 (EAS1)	Data obtained during Double-Blind Period from the mITT population, excluding data after initiating rescue antihyperglycemic medication or discontinuing from study intervention.
Efficacy Analysis Set 2 (EAS2)	Data obtained during Double-Blind Period and Open-Label Period from the mITT population, excluding data after initiating rescue antihyperglycemic medication or discontinuing from study intervention.
Full Analysis Set (FAS)	Data obtained during Double-Blind Period from the mITT population, regardless of adherence to study intervention or initiation of rescue antihyperglycemic medication.

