GLP-1R, GIP Cross-Reactive, In Silico Neutralizing to Native Treatment, LY	
GIP, GLP-1 Cross-Reactive and In Silico Neutralizing to Treatment Plus	
Native GLP-1 Present at baseline, Postbaseline TE ADA+, Follow-up)	
Neutralizing TZP for GIPR, GIPR Inconclusive, GLP-1R,	
GLP-1R Inconclusive, GIP Cross-Reactive, GLP-1 Cross-	
Reactive	
Summary of TE ADA Within the participants evaluable for TE ADA, the count and Immunogenicity	
Persistence for all TE ADA percentages of the following will be summarized: Analysis Set 2 (LY	Υ
Evaluable Tirzepatide- Persistence (Persistent, Potential Persistent, Transient) of Treatment, LY	
Treated Participants TE ADA+ participants, TE ADA- patients Treatment Plus	
Follow-up)	
Maximum Titer Distribution The distribution of the maximum titer values for the Immunogenicity	
of TE ADA+ Participants TE ADA+ participants will be summarized. Analysis Set 2(LY)	
Treatment)	1
· ·	
Summary of Time to First TE A summary table of time to first TE ADA+ titer in TE ADA Immunogenicity	
ADA+ Titer among evaluable participants will be examined by study and Analysis Set 2 (LY	·Υ
Tirzepatide-Treated TE ADA treatment group via cumulative categories (≤ 4 week, ≤ 12 Treatment)	
Evaluable Participants week, \leq 30 week, \leq 42 week, \leq 52 week, and \leq 56 week).	
Summary of Change of Analyses on the primary endpoint (change in HbA1c from Immunogenicity	
Tirzepatide-Treated baseline at Week 30), guided by the efficacy estimand, will be Efficacy Set	
Participants in HbA1c from presented visually in the form of boxplots and will include	
Baseline at Primary Visit by summary statistics for subgroups using TE ADA Status and	
TE ADA Status neutralizing TZP against GIPR and GLP-1R.	

Abbreviations: ADA = antidrug antibodies; GIP = glucose-dependent insulinotropic polypeptide; GIP-1 = glucose-dependent insulinotropic polypeptide receptor; GLP-1R = glucagon-like peptide-1 receptor; HbA1c = glycated hemoglobin; Nab = neutralizing antibodies; TE = treatment-emergent; TE ADA = treatment-emergent antidrug antibodies; TZP = tirzepatide.

Safety analysis:

A summary will be provided of the count and percentage of tirzepatide-treated participants experiencing specific TEAEs (Hypersensitivity reactions [see Section 4.6.6.6], Injection site reactions [see Section 4.6.6.7]) by participant TE ADA status (TE ADA+, TE ADA-, and TE ADA Inconclusive). These summaries will utilize data from Immunogenicity Analysis Sets 1. and 2 (LY Treatment).

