4.9. Changes to Protocol-Planned Analyses

Refer to revision history.

5. Sample Size Determination

The statistical power calculation assumes that the evaluation of superiority of pooled tirzepatide 5 mg and 10 mg QW against placebo will be conducted at a 2-sided significance level of 0.05, relative to the primary endpoint (change in HbA1c from baseline at 30 weeks) in an analysis utilizing all data, on or off intervention. Additionally, it assumes a 1.1% greater mean reduction in HbA1c (placebo adjusted) for pooled tirzepatide (5 mg and 10 mg) at Week 30 visit, and a common SD of 1.5% from change in HbA1c at Week 30 visit.

Based on these assumptions, randomizing at least 90 participants in a 1:1:1 ratio to each study arm will provide 90% power to demonstrate superiority of the pooled tirzepatide 5 mg and 10 mg to placebo.

6. Supporting Documentation

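### The SAP's only HbA1c-by-antibody summary is limited to on-drug, pre-rescue Week 30 completers, so a loss of effect due to antibodies can be understated

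*SAP*

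**What the plan says.** SAP 4.6.6.8.2 (Table GPGV.4.8) bases the antibody-efficacy set on TE ADA-evaluable mITT participants, as a subset of EAS1, with the restriction "This analysis set includes only Week 30 completers". The row label is lost in the text available. It is the only EAS1-based row, so it must be the Immunogenicity Efficacy Set named in Table GPGV.4.9. The SAP does not define a Week 30 completer.

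EAS1 (SAP Section 3, Table GPGV.3.1) takes double-blind data "excluding data after initiating rescue antihyperglycemic medication or discontinuing from study intervention".

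Table GPGV.4.9 (SAP 4.6.6.8.5) uses this set for Week 30 HbA1c change under the efficacy estimand, as boxplots with "summary statistics for subgroups using TE ADA Status and" neutralising status at each receptor. No model or test is attached.

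Protocol 9.3.6 leaves further work optional: "The relationship between the presence of antibodies and tirzepatide PK and PD response including safety and efficacy to tirzepatide may be assessed".

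**The concern.** Whether a child stays in this comparison depends partly on the outcome being compared. Rescue is triggered by persistently high fasting glucose (Protocol 8.3.3.2). If antibodies blunt the drug in some children, those children are the likelier ones to be rescued, and a rescued child has no Week 30 value in EAS1. The antibody-positive group then loses more of its poor responders than the antibody-negative group, and the difference shrinks.

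The main efficacy-estimand analysis of HbA1c is less exposed to this. Its MMRM (SAP 4.1.5.1 and 4.3.1) keeps each non-completer's values up to the event and relies on missing at random. The antibody summary names the same estimand, which concerns all participants as if adherent and unrescued, but shows only those with an observed, on-drug, pre-rescue Week 30 value.

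At stake is a reassuring statement that antibodies do not affect efficacy, drawn from a display that favours it and does not show how many children in each antibody group were left out, or why.

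**Working it through.** **1. The plan's own figure.** SAP Section 5 has a test "conducted at a 2-sided significance level of 0.05, relative to the primary endpoint", a "1.1% greater mean reduction in HbA1c (placebo adjusted) for pooled tirzepatide", "a common SD of 1.5% from change in HbA1c at Week 30 visit", and "randomizing at least 90 participants in a 1:1:1 ratio to each study arm", that is 60 pooled tirzepatide against 30 placebo. Noncentrality = 1.1 / (1.5 × √(1/30 + 1/60)) = 1.1 / 0.335 = 3.28. With 88 degrees of freedom, power is 90.0% (90.7% by the normal approximation). The stated 90% reproduces. The documents give no figure for the antibody summary, so 1.1 and 1.5 are borrowed below as scale.

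**2. What happens to a rescued or stopped child.**
- Protocol 6.8.1: a rescued child continues in the study.
- Protocol 7.1: a child who stops drug remains and completes all visits.
- Protocol 1.3: double-blind HbA1c is drawn at Weeks 0, 4, 8, 12, 16 and 30, and ADA at Weeks 0, 4, 12 and 30.
- SAP 4.6.6.8.4: a baseline ADA result and one later result make a child TE ADA-evaluable.

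Such a child will often have an antibody status and a measured Week 30 HbA1c, yet contributes nothing to the boxplot. The SAP plans no FAS version by antibody status and no count of rescue or discontinuation by antibody status. Its adverse-event summaries by ADA status cover only hypersensitivity and injection site reactions.

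**3. Attenuation under a threshold model.** Assumptions: antibodies cost the full L = 1.1 points on average; SD S = 1.5 in both groups; one latent glycaemic variable, with correlation r to Week 30 HbA1c change, governs exclusion in both groups; its cut-off c excludes a share f of antibody-negative children, so Φ(c) = 1 − f. Write a = c − rL/S.
- Retained mean, negatives (true mean 0): −S·r·φ(c)/Φ(c)
- Retained mean, positives (true mean L): L − S·r·φ(a)/Φ(a)
- Share of positives excluded: 1 − Φ(a)

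Example, f = 0.05 and r = 0.7: c = 1.645 and a = 1.645 − 0.7 × 1.1/1.5 = 1.132. Positives excluded: 12.9%. Retained means: −0.114 and 0.846. Observed difference: 0.96 instead of 1.10, so 13% is lost.

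| Negatives excluded | r = 0.5 | r = 0.7 | r = 0.9 |
|---|---|---|---|
| 3% | 1.05 | 0.99 | 0.91 |
| 5% | 1.03 | 0.96 | 0.85 |
| 10% | 1.01 | 0.90 | 0.76 |

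Between 69% and 95% of the 1.10 stays visible.

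**4. Other model shapes.**
- *Exclusion directly on the Week 30 change* (negatives' mean −1.1, SD 1.5, excluded above +0.5 to +2.0 points): a loss of 1.1 appears as 0.60 to 0.90, 0.55 as 0.33 to 0.47, and 0.30 as 0.19 to 0.26. That keeps 54% to 88%.
- *Mixture*: a share p of antibody-positive children lose all 1.1, and a share q of those are excluded. Observed loss = p(1 − q) × 1.1 / (1 − pq), against a true p × 1.1. With p = 0.3 the true loss is 0.33; it appears as 0.31, 0.27, 0.19, 0.11 and 0.00 for q = 0.10, 0.25, 0.50, 0.75 and 1.00. It reaches zero only when every affected child is excluded.

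**5. Precision.** With 60 tirzepatide children and an assumed 20% to 50% antibody-positive, the 95% half-width of the contrast is 1.96 × 1.5 × √(1/12 + 1/48) = 0.95 down to 1.96 × 1.5 × √(1/30 + 1/30) = 0.76 points.

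**The case against.** A reader might infer that a true loss of effect is hidden. The documents do not support that. Rescue needs an average fasting glucose above 270, 240 or 200 mg/dL, depending on the week, over two consecutive weeks and after a compliance check (Protocol 8.3.3.2). Many children with a blunted effect would stay below that and remain in the boxplot. Lack of efficacy is not a listed reason to stop drug (Protocol 7.1), and stops for gastrointestinal intolerance (6.5.4) need not follow loss of effect. One threshold for both rescue and stopping is therefore a modelling convenience, and a full 1.1-point loss in antibody-positive children is an extreme input.

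The attenuation is also small beside the noise: 0.14 to 0.20 points in the middle cases, against a half-width of 0.76 to 0.95. That is true, but a biased and imprecise contrast is all the easier to read as no difference.

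Dropping post-rescue values follows from the efficacy estimand, and a boxplot of observed EAS1 values at Week 30 cannot show a child who has none, so the completer sentence adds little to EAS1. This stands. What remains is that nothing replaces the missing values, whereas the main analysis has the MMRM.

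Some of the information can be recovered. TE ADA counts on Immunogenicity Analysis Set 1 are kept regardless of rescue or adherence, and subtracting the boxplot numbers gives how many were lost. SAP 4.2 and 4.6.6.2 plan discontinuation counts and a rescue listing. None of these gives the reason by antibody status. The separate PK/PD plan (SAP 4.7.4) was not available and may contain related work, so the statement that this is the only such analysis applies to the SAP.

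**Conclusion.** The point holds as a limitation of one descriptive summary. Children rescued or stopped before Week 30 drop out of the SAP's only HbA1c-by-antibody display. To the extent that rescue follows loss of effect, the antibody contrast is biased towards no difference. Under the threshold model the understatement is about 5% to 31% of the loss; direct truncation gives 12% to 46%; full masking occurs only in the limiting case where every affected child is excluded. All of these rest on assumed exclusion rates, correlations and loss sizes, because the documents give no antibody prevalence and no rescue or stopping rates by antibody status. The actual size is unknown.

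A reader might also infer that the trial's efficacy conclusion is affected. It is not: the summary has no test, sits outside the multiplicity scheme and does not feed any primary or key secondary analysis.

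**What to change.** In SAP 4.6.6.8.2 and 4.6.6.8.5:
- Keep the planned boxplot, and state what counts as a Week 30 completer.
- Add the same Week 30 HbA1c summary by TE ADA and NAb status on FAS, for all TE ADA-evaluable participants randomised to tirzepatide.
- Beside both, tabulate by TE ADA and NAb status the number rescued, the number who discontinued study intervention, and the number without a usable Week 30 value.
- Optionally, show the last on-drug, pre-rescue HbA1c change from EAS1 with its visit week. That value may fall during dose escalation, which takes 12 weeks for the 10 mg arm (Protocol 4.2), so it should not stand alone.

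The cost is SAP wording, one more boxplot and one count table, all from data already scheduled for collection. The downside is small: FAS values include the effect of rescue therapy, which can itself lower Week 30 HbA1c and mask a loss, so neither version is clean and the two must be read together with the counts.

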4.6.6.8.3. Definitions of Immunogenicity Assessment Periods

Immunogenicity Baseline Observations: The baseline period for immunogenicity assessment for each participant includes all observations up to the first dose of study treatment. In instances where multiple baseline observations are collected, to determine participant ADA status the last nonmissing immunogenicity assessment prior to first administration of study drug is used to determine treatment-emergent status (see below).

Immunogenicity Postbaseline Period Observations: Postbaseline period observations for each participant include all observations after the first administration of study drug.

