4.1.1. Baseline Definition

Unless specified otherwise, the last measurement during Visit 1 to Visit 3 (including unscheduled visits) collected prior to or on the first dose day will serve as baseline.

- Immunogenicity data collected up to the first dose time will serve as baseline.
- Vitals, labs and ECG baseline needs to be prior to or within 1 hour after the first dose time.
- Patient-reported outcomes data collected at Visit 3, regardless of the timing relative to first dose, will serve as baseline.

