4.6.6.8.4. Definitions of Participant ADA Status

TE ADA-evaluable participants: A participant is evaluable for TE ADA if the participant has a nonmissing baseline ADA result and at least 1 nonmissing postbaseline ADA result.

TE ADA-unevaluable participant: any participant who does not meet the evaluable criteria.

Baseline ADA Present (preexisting antibody): ADA detected in a sample collected up to the first dose date and time.

Baseline ADA Not Present: ADA is not detected, and the corresponding PK concentration is missing or below the drug tolerance limit in a sample collected up to the first dose date and time.

TE ADA+ participant: An evaluable participant who had a:

- baseline status of ADA Not Present and at least 1 postbaseline status of ADA Present with titer $\ge 2 \times$ the MRD of the ADA assay.
- baseline and postbaseline status of ADA Present, with the postbaseline titer being 2 dilutions (4-fold) greater than the baseline titer. That is, the participant has baseline status of ADA Present, with titer 1:B, and at least 1 postbaseline status of ADA Present, with titer 1:P, with P/B ≥4.

As shown in Figure GPGV.4.1, a titer is expected when the ADA assay result is Detected. On the occasion, when the corresponding assay cannot be performed, in which case a titer value will be imputed for the purpose of TE ADA determination. A baseline sample with detected ADA and no titer is imputed to be the MRD (1:10), and a postbaseline sample with ADA detected and no titer is imputed to be 1 dilution above the MRD (1:20).

TE ADA-Inconclusive participant: A TE ADA evaluable participant is TE ADA Inconclusive if ≥20% of the participant's postbaseline samples, drawn predose, are ADA Inconclusive and all remaining postbaseline samples are ADA Not Present.

TE ADA-negative (TE ADA-) participant: A TE ADA-evaluable participant is TE ADA- when the participant is not TE ADA+ and not TE ADA Inconclusive.

For each NAb assay, the following are defined:

NAb+ participant: A participant who is TE ADA+ and has a NAb+ sample in the postbaseline period.

NAb Inconclusive participant: A participant who is TE ADA+ but not NAb+, and all samples that have TE ADA+ titer have a NAb Inconclusive sample result.

Nab negative (NAb-) participant: A participant is who is neither NAb+ nor NAb Inconclusive.

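### Participants who switch from placebo keep a pre-placebo antibody baseline in Immunogenicity Analysis Set 2, so samples drawn before any tirzepatide can decide their tirzepatide TE ADA status.

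*SAP*

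**What the plan says.** SAP section 4.6.6.8.3 defines the antibody baseline: "The baseline period for immunogenicity assessment for each participant includes all observations up to the first dose of study treatment". It continues: "Postbaseline period observations for each participant include all observations after the first administration of study drug". Section 4.1.1 makes the same cut ("Immunogenicity data collected up to the first dose time will serve as baseline"), inside a general definition whose window ends at Visit 3. Section 4.6.6.8.4 defines pre-existing antibody as "ADA detected in a sample collected up to the first dose date and time".

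Table GPGV.4.8 describes the tirzepatide-treated set, Immunogenicity Analysis Set 2, as "Participants who had at least one dose of tirzepatide". Its LY Treatment Period is defined as the double-blind plus the open-label period, and a second version adds safety follow-up. Under SAP section 1.2.3, participants randomized to placebo start tirzepatide when the open-label period begins.

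Section 4.6 makes clear that randomized study treatment can be tirzepatide or placebo. For the placebo/tirzepatide 5 mg arm it then moves the overall-study baseline to the first tirzepatide dose, for two kinds of analysis: TEAEs, and categorical analyses of laboratory, vital-sign and ECG data. It does not mention antibodies.

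**The concern.** The incidence of treatment-emergent antibodies to tirzepatide is a listed safety endpoint (SAP section 1.1). For a switcher the first study dose is placebo. Read together, the definitions make 30 weeks of placebo data postbaseline in an analysis of tirzepatide-treated participants. A sample that cannot reflect tirzepatide may then set the status.

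The consequences go beyond the incidence table. Neutralizing-antibody status depends on TE ADA status. The Set 2 summaries of hypersensitivity and injection site reactions by TE ADA status combine an adverse-event baseline that has been reset with an antibody baseline that has not, in the same people. The table of time to first TE ADA+ titer states no origin. If it runs from the first study dose, about 30 weeks before tirzepatide are included for this group.

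**Working it through.** The plan states no figure on this point, so the check applies its rules to example profiles.

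**Inputs**
- Antibody samples: Weeks 0, 4, 12 and 30 (Visits 3, 5, 8 and 13; Protocol 1.3.1), then Weeks 42, 52 and 56 (Visits 17, 19 and 801; Protocol 1.3.2). They are taken before dosing.
- First tirzepatide dose for switchers: after the Week 30 sample.
- Allocation: 1:1:1 of at least 90 (SAP 1.2.2).
- Rules in SAP 4.6.6.8.4, with minimum required dilution (MRD) 1:10. TE ADA+ needs one postbaseline titer of at least 2 × MRD = 1:20 if baseline is negative, or a ratio to baseline of at least 4 if baseline is positive. A detected sample with no titer is set to 1:10 at baseline and to 1:20 postbaseline. A participant is Inconclusive "if ≥20% of the participant's postbaseline samples, drawn predose, are ADA Inconclusive" and "all remaining postbaseline samples are ADA Not Present".

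**Exposure to the problem**
- LY Treatment Period: Weeks 4, 12 and 30 out of 4, 12, 30, 42 and 52, so 3/5 = 60% of postbaseline samples precede tirzepatide.
- With follow-up: 3/6 = 50%.
- Share of Set 2: 30/90 = 33% at most, before any dropout by Week 30.

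**Status under the two baselines** (LY Treatment Period; samples not listed are Not Present)

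| Profile | As written (baseline Week 0) | Baseline at last sample before tirzepatide (Week 30) |
|---|---|---|
| 1:20 at Week 12 only | TE ADA+ | TE ADA- |
| Week 30 detected, no titer | imputed 1:20, TE ADA+ | baseline imputed 1:10, TE ADA- |
| 1:20 at Week 30, unchanged on tirzepatide | TE ADA+ | 20/20 = 1, below 4, TE ADA- |
| 1:80 at Week 0, falling to 1:10 at Week 30, then 1:40 | 40/80 = 0.5, TE ADA- | 40/10 = 4, TE ADA+ |
| 1:10 at Week 12, Week 42 inconclusive | 1/5 = 20%, but Week 12 is Present, TE ADA- | 1/2 = 50%, Inconclusive |
| No sample taken after Week 30 | evaluable, TE ADA- | unevaluable |
| Never positive | TE ADA- | TE ADA- |
| First positive after the switch (1:40) | TE ADA+ | TE ADA+ |

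In the fifth row the flip comes from the Present sample, not from the percentage. Without the Week 12 positive, the participant is Inconclusive both ways. These ratios count Week 52 as predose. If it is excluded, because dosing stops at Visit 19, they become 1/4 = 25% and 1/1 = 100%, and the flip remains. Week 56 is left out for the same reason. If it counted, a switcher with one inconclusive Week 42 sample and all others negative would go from 1/6 = 16.7% (TE ADA-) to 1/3 (Inconclusive).

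**Possible size.** The documents give no antibody rate on placebo. As an assumption, let 1% to 10% of 30 switchers first meet the titer rule on placebo:
- expected number: 30 × 0.01 = 0.3 to 30 × 0.10 = 3;
- chance of at least one: 1 − 0.99^30 = 26% to 1 − 0.90^30 = 96%;
- share of 90 tirzepatide-treated participants: 0.3/90 = 0.3% to 3/90 = 3.3%.

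**Time to first TE ADA+.** From Visit 13 to Visit 17 is 42 − 30 = 12 weeks nominally, or 10 to 14 weeks when both visits use their ±7-day windows. On a clock from the first study dose, the same first tirzepatide-period sample falls at Week 42.

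**The case against.** The strongest reply is that section 4.6 already covers this. Set 2 is a subset of the overall-safety set SS2, immunogenicity sits within the safety section, the protocol lists anti-drug antibody among its laboratory tests, and TE ADA status is categorical. On that view the laboratory reset applies. It does not carry, because section 4.1.1 lists immunogenicity apart from vitals, labs and ECG with its own baseline, and section 4.6.6.8.3 is the more specific rule.

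A second reply is that a period named after LY, the tirzepatide code, means time on tirzepatide. The written definition includes the double-blind period and makes no exception for switchers, so the label cannot override it. The name may still show what was intended, in which case one sentence settles the matter.

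Three points stand as limits. First, Table GPGV.4.9 presents time to first TE ADA+ by treatment group in categories up to 4, 12, 30, 42, 52 and 56 weeks. These match the sampling weeks, so if the clock runs from the first study dose, switchers first positive on placebo would show mainly in the categories up to 30 weeks. That table would reveal part of the problem; the incidence and by-status tables would not. Second, these outputs carry no type I error control, and no groups are compared at Week 52. Third, the reset has a cost of its own: in the profile falling from 1:80 to 1:10, the participant becomes TE ADA+ at 1:40, below the pre-study titer.

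**Conclusion.** The point holds. Followed as written, the SAP lets samples that precede all tirzepatide determine a switcher's tirzepatide TE ADA status, evaluability and Inconclusive status. This conflicts with the SAP's own reset for the same arm. Up to 3 of 5 deciding samples are affected (3 of 6 with follow-up), in at most about one third of Set 2.

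Errors can go both ways, and neither the number nor the net direction can be derived; the range of 0.3 to 3 participants rests on the assumed rate of 1% to 10%. Profiles that need a missing titer or no sample after the switch should be uncommon, since samples are also drawn at early termination and at Visit 801.

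The effect is limited to the Placebo/TZP 5 mg group and to any total or by-status summary over all tirzepatide-treated participants. That scope is inferred mainly from the treatment groups in SAP 4.1.4, because Table GPGV.4.9 does not set out its columns. TZP 5 mg, TZP 10 mg, TZP_ALL, Set 1 and the primary HbA1c analysis are not affected. The row label in Table GPGV.4.8 is incomplete in the text as read; it is identified as Set 2 because Table GPGV.4.9 uses that name with the same periods. The change should be made, but it does not bear on the efficacy conclusions.

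**What to change.** Add one rule for participants randomized to placebo, in Set 2 only, to sections 4.1.1, 4.6.6.8.3 and 4.6.6.8.4 and to Table GPGV.4.8:

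- Baseline is the last non-missing antibody result before the first tirzepatide dose, normally the Visit 13 predose sample.
- Only later samples are postbaseline, for TE ADA status, evaluability and the Inconclusive rule.
- The LY Treatment Period starts at the first tirzepatide dose.
- In Table GPGV.4.9, time to first TE ADA+ runs from the first tirzepatide dose.
- Visit 3 antibody status is shown alongside for this group.
- Set 1 stays as it is.

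It would also help to state whether the Week 52 and Week 56 samples count as predose.

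The cost is SAP text and derivation code, with no new sampling. Switchers with no sample after starting tirzepatide become unevaluable in Set 2. If the Visit 13 sample is missing, an earlier one has to serve. A participant whose Visit 3 antibody has disappeared by Week 30 and returns on tirzepatide could be classed as treatment-induced, which is why Visit 3 status should be displayed.
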